1.2.4 Clinical Pharmacology

Final PK data are available for 3 monotherapy studies (KRN951/03-B01, AV-951-07-201, and AV-951-08-105) and 2 combination therapy studies (AV-951-07-102 and AV-951-08-104) in subjects with cancer. Additionally, final PK data are available for 2 healthy volunteer studies (Studies AV-951-09-109 and AV-951-10-111).

In summary, across studies, median time to peak serum concentration, (tmax), of tivozanib (free base), ranges from about 2 to 24 h with substantial variability between subjects. In studies from healthy volunteers with detailed sampling regimens in the first 24 h, median Tmax is 10 h. Across the multiple studies, exposure (Cmax and AUC) of tivozanib (free base) generally increases in a roughly dose proportional manner and accumulation at steady-state is approximately 6-7 times single dose levels. This accumulation is consistent with the long t1/2 of tivozanib (free base), the mean between studies being approximately 3.6 to 4.7 days. Also, the PK of tivozanib (free base) is similar in oncology patients compared to the profile in healthy volunteers.

In combination studies of tivozanib hydrochloride with temsirolimus (AV-951-07-102) and in another with paclitaxel (AV-951-08-104), there was no indication of a PK interaction that influenced tivozanib (free base) levels or those of the coadministered agent. Data from the mass balance study (Study AV-951-10-111) found that 79.3% of the total radioactivity was recovered from feces. Urine contained no detectable tivozanib (free base) but various metabolites were detected in urine and accounted for 11.8% of recovered radioactivity. The findings are consistent with elimination of tivozanib (free base) via feces and some degree of metabolism.

In vitro data suggest the possibility that tivozanib hydrochloride may interact with CYP3A4 inducers and/or inhibitors. Formal drug-drug interaction studies are currently underway to assess whether such interactions may be clinically relevant. Data are not yet available from these studies [6].

1.2.5 Drug-Drug Interaction Studies

Results from drug-drug interaction studies conducted in vitro indicate that tivozanib hydrochloride had no inhibitory effect on CYP3A4, CYP2C8, CYP2D6, CYP1A2, CYP2C9, or CYP2C19. Further, tivozanib hydrochloride did not show any propensity to induce CYP450 isoforms in an in vitro assay system at clinically relevant exposures. Due to the low likelihood of tivozanib hydrochloride causing a drug-drug interaction by inhibiting the metabolism of a co-administered agent, no clinical studies to evaluate this question are planned.

In vitro studies with cDNA-derived CYP450 showed that only CYP1A1 (primarily extrahepatic) and CYP3A4 were capable of metabolizing tivozanib hydrochloride. Clinical trials in healthy volunteers investigating the effect of ketoconazole (AV-951-11-116) and rifampin (AV-951-11-117) are in progress [6].

1.3 Study Rationale

1.3.1 Angiogenesis and Tumor Growth

Angiogenesis is defined as the formation of new blood vessels from preexisting vasculature. Angiogenesis is classified into 2 types: physiologic and pathologic. Physiologic angiogenesis includes embryonic development, reproduction, and wound healing. Pathologic angiogenesis is involved in diseases such as cancer, rheumatoid arthritis, and diabetic retinopathy. Angiogenesis plays an important role in the control of cancer progression and metastasis. Tumors cannot grow beyond 2 to 3 mm³ in size in the absence of the new vascularization. While angiogenesis is a complex process involving endothelial cell proliferation, survival migration, vessel morphogenesis and maturation, signaling through endothelial growth factors such as the VEGF ligands is known to be rate limiting for angiogenesis. Inhibiting tumor angiogenesis is believed to be a promising therapeutic modality [12].

1.3.1.1 Vascular Endothelial Growth Factor Pathway

The vascular endothelial growth factor (VEGF) signaling pathway appears to be the dominant pathway involved in tumor angiogenesis. The VEGF family consists of five structurally related proteins (VEGF-A, VEGF-B, VEGF-C, VEGF-D and Placental Growth Factor (PLGF), and signaling through this pathway is mediated by the binding of these growth factors to three receptors (VEGFR-1, VEGFR-2, and VEGFR-3). The ligands bind each receptor with distinct but overlapping specificity as well as distinct biological function, together acting to effect proliferation, migration and morphogenesis of endothelial cells to form functional vasculature [13].

1.3.1.2 Vascular Endothelial Growth Factor Receptor

Two high-affinity cognate endothelial receptors for VEGF have been identified. One is VEGF receptor-1 (VEGFR-1, also known as Flt1) and the other is VEGFR-2 (also known as kinase insert domain-containing receptor (KDR)/Flk1). These receptors have a characteristic structure with 7 immunoglobulin-like domains in the extracellular domain and a cytoplasmic tyrosine kinase domain with a long kinase insert region. They are members of a large family of receptor tyrosine kinases and are localized on endothelial cells. Activation of VEGFR-1 and VEGFR-2 receptors occurs through ligand binding, which facilitates receptor dimerization and autophosphorylation of tyrosine residues. VEGFR-2 is considered the major mediator of the mitogenic, angiogenic and permeability-enhancing effects of VEGF. In addition, recent studies have also suggested the role of VEGFR-3 (FLT-4), another tyrosine kinase, in tumor angiogenesis. VEGFR-3 is expressed in the tumor vasculature and targeting its activity is known to retard tumor formation by inhibiting angiogenesis [14].

Tivozanib hydrochloride is a highly potent, selective inhibitor of the

receptor tyrosine kinase activity of VEGFR-1, 2, and 3. It has been shown to block various VEGF-induced biologic responses in endothelial cells in vitro. Furthermore, tivozanib hydrochloride demonstrated a marked antitumor activity against human tumor xenograft models in nude mice and nude rats. Tivozanib hydrochloride has good pharmacokinetic profiles in various animal models. In toxicology studies conducted using Good Laboratory Practices, toxicities were similar across species, were generally dose responsive and showed signs of recovery following cessation of treatment. Tivozanib hydrochloride has exhibited significant anti-tumor effects against a wide variety of tumors in rat and mouse xenograft models. Pharmacologic studies showed that tivozanib hydrochloride is a potent inhibitor of VEGFR phosphorylation, which plays a major role in tumor angiogenesis and vascular permeability, but does not have obvious direct tumorcidal activity. These data indicated that the mechanism of the anti-tumor activity for tivozanib hydrochloride is through the inhibition of tumor angiogenesis and vascular permeability [6].

1.3.2 Rationale for Clinical Trial Design

This is a single arm phase II trial. All patients will receive 1.5 mg orally of tivozanib given daily for 3 weeks with one week off to complete a 4 week cycle. At the start of each cycle, patients will have a visit with a clinician who will obtain a pertinent history, perform a physical exam, draw serum CA-125 values and a CBC and CMP and determine if the patient is appropriate for therapy. Treatment will continue until documented disease progression or the patient is unable to tolerate further therapy due to excessive toxicity.

2 STUDY OBJECTIVES

2.1 Primary

The primary objective of this single-arm, phase II clinical trial will be to determine the clinical activity of tivozanib in patients with platinum-resistant, recurrent ovarian, fallopian tube or primary peritoneal cancer. For this protocol text, these disease entities will be referred to collectively as ovarian cancer. The primary endpoint of this trial will be the overall response rate of patients with platinum-resistant ovarian cancer to treatment with single agent tivozanib as measured by physical exam findings, serum CA-125 levels and/or measurement of index lesions via appropriate imaging studies using RECIST criteria.

2.2 Secondary

- 2.2.1 The secondary objectives of this trial will include determining the potential survival advantage and characterizing the safety of single agent tivozanib in patients with platinum-resistant ovarian cancer.
- 2.2.2 The secondary endpoints will include the duration of progression-free survival in patients with platinum-resistant ovarian cancer treated with single agent tivozanib.

Additionally, toxicity will be reported using Common Terminology Criteria for Adverse Events (CTCAE) version 4.03.

2.3 Exploratory

- 2.3.1 The first exploratory endpoint is a retrospective analysis of archival tissue from all patients who have enrolled to measure the expression of proteins that play a role in VEGF signaling and other relevant oncogenic pathways. The level of expression will be correlated with the best response to treatment (CR, PR, SD, PD).
- 2.3.2 The second exploratory endpoint is a retrospective analysis of genetic reports from all patients who have enrolled, if available. This analysis will be used to correlate genetic mutation burden with response to treatment.

3 PATIENT SELECTION

The target population for this study is patients with recurrent or persistent, platinum resistant epithelial ovarian, fallopian tube or primary peritoneal carcinoma. This will be a multicenter trial conducted at Northwestern Medicine. Northwestern University will serve as the lead site and coordinating center for this study. Participating sites will include Northwestern Medicine Cancer Center Warrenville and the Northwestern Medicine Cancer Center Delnor and Northwestern Lake Forest Hospital.

A total of 30 subjects will be needed for this trial. Approximately 6 potentially eligible patients are seen per month, and it is anticipated that at least 3 per month will be accrued (once all sites are up and running). Potential patients may be referred to the Principal Investigator (PI) at Northwestern University, [name], at [contact], or to the local PI at each participating site.

Eligibility will be evaluated by the study team according to the following criteria. Eligibility waivers are not permitted. Subjects must meet all of the inclusion and none of the exclusion criteria to be registered to the study. Study treatment may not begin until a subject is registered. Please refer to Section 10 for complete instructions regarding registration procedures.

3.1 Inclusion Criteria

Each patient must meet all of the following inclusion criteria to be enrolled in the study:

- 3.1.1 Patients must have recurrent or persistent, platinum resistant or refractory epithelial ovarian, fallopian tube or primary peritoneal carcinoma. Platinum-resistant disease is defined as a recurrence within 6 months of completing platinum-based chemotherapy.
- 3.1.2 Patients must have measurable disease or non-measurable (detectable) disease:
 - Measurable disease is defined as at least one lesion that can be accurately measured in at least one dimension (longest diameter to be recorded). Each lesion must be greater than or equal to 10 mm when measured by CT, MRI or by clinical exam; or greater than or equal to 20 mm when measured by chest x-ray. Lymph nodes must be greater than or equal to 15 mm in short axis when measured by CT or MRI.

- Non-measurable (detectable) disease in a patient is defined in this protocol as one who does not have measurable disease based on RECIST criteria but does have a CA-125 greater than or equal to two times the upper normal limit within the last 60 days (confirmatory at baseline) and at least one of the following conditions:
 - Ascites and/or pleural effusion attributed to tumor
 - Hypermetabolic lesions on PET Scan
- 3.1.3 Patients with measurable disease must have at least one target lesion as defined by RECIST 1.1 to be used to assess response on this protocol.
- 3.1.4 Patients must have an ECOG Performance Status of 0, 1, or 2.
- 3.1.5 Patients must have had one prior taxane and platinum-based chemotherapeutic regimen for management of primary disease containing carboplatin, cisplatin, or another organoplatinum compound. This initial treatment may have included intraperitoneal therapy, consolidation, non-cytotoxic (biologic/targeted agents) or extended therapy administered after surgical or non-surgical assessment. There is no maximum number of prior regimens.

Note: Use of bevacizumab as maintenance therapy after initial adjuvant platinumbased chemotherapy is allowed so long as platinum-resistant recurrence occurred subsequent to a separate platinum-based regimen AND more than 6 months after completion of bevacizumab maintenance.

- 3.1.6 Patients must have signed an approved informed consent and authorization permitting the release of personal health information.
- 3.1.7 Patients must be willing and able to complete all study procedures.
- 3.1.8 Patients must have adequate organ or bone marrow function within 28 days prior to study registration, as defined below:

Hemoglobin	\geq 9.0 g/dL
Absolute neutrophil count	$\geq 1500 \text{ per mm}^3$
(ANC)	
Platelet count	$\geq 100,000 \text{ per mm}^3$
Total bilirubin ¹	\leq 1.5 × ULN (or \leq 2.5 x ULN for subjects
	with asymptomatic Gilbert's syndrome)
Aspartate aminotransferase	\leq 2.5 × ULN (or \leq 5 × ULN for subjects
(AST) or alanine	with liver metastasis)
aminotransferase (ALT) ¹	
Alkaline phosphatase	\leq 2.5 × ULN (or \leq 5 × ULN for subjects
	with liver or bone metastasis)
Creatinine	\leq 2.0 × ULN;
PT/ PTT	PT such that INR \leq 1.5 x ULN (unless a
	patient is on therapeutic warfarin) or a
	$PTT \le 1.5 \text{ x ULN}$
Proteinuria	\leq 2+ by urinalysis or urine dipstick

- 1. Also excluded are patients with elevations in BOTH total bilirubin > ULN AND AST or ALT > ULN
- 3.1.9 Patients must be greater than or equal to 18 years of age.
- 3.1.10 Females of child-bearing potential (FOCBP) and males must agree to use adequate contraception (male or female condoms, diaphragms, and spermicides, which are creams or gels that contain a chemical to kill sperm) prior to study entry, for the duration of study participation, and for 45 days following completion of therapy.

NOTE: A FOCBP is any woman (regardless of sexual orientation, having undergone a tubal ligation, or remaining celibate by choice) who meets the following criteria:

- Has not undergone a hysterectomy or bilateral oophorectomy
- Has had menses at any time in the preceding 12 consecutive months (and therefore has not been naturally postmenopausal for > 12 months)
- 3.1.11 FOCBP must have a negative pregnancy test within 7 days prior to registration on study.
- 3.1.12 Patients must have the ability to understand and the willingness to sign a written informed consent prior to registration on study.

3.2 Exclusion Criteria

Patients meeting any of the following exclusion criteria are not to be enrolled in the study:

- 3.2.1 Patients who have had previous treatment with tivozanib are excluded.
- 3.2.2 Patients with symptomatic left ventricular dysfunction or baseline left ventricular ejection fraction (LVEF) my multigated acquisition scan (MUGA) or echocardiogram (ECHO) of \leq 50% are not eligible.
- 3.2.3 Patients with uncontrolled hypertension as defined as systolic blood pressure of >140mmHg or diastolic blood pressure of >90mmHg documented on 2 consecutive measurements taken at least 24 hours apart are not eligible. *Note: Initiation or adjustment of antihypertensive medication(s) is permitted prior to study entry. Following antihypertensive medication initiation or adjustment, blood pressure (BP) must be re-assessed three times at approximately 2-minute intervals. At least 24 hours must have elapsed between anti-hypertensive medication initiation or adjustment and BP measurement. These three values will be averaged to obtain the mean diastolic blood pressure and the mean systolic blood pressure. The mean SBP / DBP ratio must be < 140/90 mmHg in order for a subject to be eligible for the study (see Table 6.1 for details on BP control and reassessment).*
- 3.2.4 Patients with significant cardiovascular disease are excluded, including:
 - Myocardial infarction, severe angina, or unstable angina within 6 months prior to administration of first dose of study drug.
 - History of serious ventricular arrhythmia (i.e., ventricular tachycardia or ventricular fibrillation).

- Cardiac arrhythmias requiring anti-arrhythmic medications (except for atrial fibrillation that is well controlled with anti-arrhythmic medication).
- Coronary or peripheral artery bypass graft within 6 months of screening.
- History of Class III or IV congestive heart failure, as defined by the New York Heart Association.
- 3.2.5 Patients with central nervous system metastases are excluded. **Note:** Subjects with previously treated (radiotherapy or surgery) brain metastasis that have been stable without steroid treatment for at least 3 months following prior treatment may be enrolled.
- 3.2.6 Any patient with a current non-healing wound, bone fracture, or skin ulcer is excluded.
- 3.2.7 Patients who are currently receiving treatment with drugs known to be strong inhibitors or inducers of isoenzyme CYP3A4 including herbal medications (See Appendix B for further information).

Note: As this list is constantly evolving, if a medication is incorrectly documented as prohibited in this protocol, documentation from the site pharmacist to the contrary will be acceptable for the purposes of registration.

- 3.2.8 Active peptic ulcer disease, inflammatory bowel disease, ulcerative colitis, or other gastrointestinal condition with increased risk of perforation; history of abdominal fistula, gastrointestinal perforation, or intra-abdominal abscess within 4 weeks prior to administration of first dose of study drug.
- 3.2.9 Serious/active infection or infection requiring parenteral antibiotics.
- 3.2.10 Patients must not have a corrected QT interval (QTc) of > 480 msec using Bazett's formula.
- 3.2.11 Patients who have had radiotherapy or minor surgical procedure within 14 days, or major surgical procedure within 28 days prior to administration of first dose of study drug are not eligible; patients with inadequate recovery from prior surgical procedure are also not eligible.
- 3.2.12 Patients with active infection requiring antibiotics are not eligible (with the exception of uncomplicated UTI and uncomplicated respiratory tract infections).
- 3.2.13 Patients may not have had any prior systemic therapy ≤ 21 days prior to registration for treatment of ovarian cancer.
- 3.2.14 Patients who have received investigational or licensed drugs that target vascular endothelial growth factor [VEGF] or VEGF receptors/pathways (such as bevacizumab, sorafenib, pazopanib, sunitinib, axitinib, cabozantinib, etc.) for the treatment of recurrent cancer are not eligible. Exceptions: prior treatment with bevacizumab in the up-front or maintenance setting is allowed, provided the patient had a favorable response to bevacizumab. Favorable response is defined as

having had a disease free interval of >6 months following completion of a bevacizumab-containing regimen. If questions, contact the PI.

- 3.2.15 Significant thromboembolic or vascular disorders within 6 months prior to administration of first dose of study drug, including but not limited to:
 - Deep vein thrombosis
 - Pulmonary embolism
 - Cerebrovascular accident (CVA) or transient ischemic attack (TIA)
 - Peripheral arterial ischemia > Grade 2 (per National Cancer Institute [NCI] Common Terminology Criteria for Adverse Events [CTCAE] Version 4.03)
- 3.2.16 Significant bleeding disorders within 6 months prior to administration of first dose of study drug, including but not limited to:
 - Hematemesis, hematochezia, melena or other gastrointestinal bleeding ≥ Grade 2 (per CTCAE Version 4.03)
 - Hemoptysis or other pulmonary bleeding ≥ Grade 2 (per CTCAE Version 4.03)
 - Hematuria or other genitourinary bleeding ≥ Grade 2 (per CTCAE Version 4.03)
- 3.2.17 Currently active second primary malignancy, including hematologic malignancies (leukemia, lymphoma, multiple myeloma, etc.), other than non-melanoma skin cancers, in situ cervical cancer, and ductal or lobular carcinoma in situ of the breast. Subjects are considered to have a currently active malignancy if they have completed anti-cancer therapy and have not been disease free for > 2 years.
- 3.2.18 Pregnant or lactating females are excluded.
- 3.2.19 Any patient with a history of genetic or acquired immune suppression disease such as human immunodeficiency virus (HIV) is excluded; subjects on immune suppressive therapy for organ transplant are also excluded.
- 3.2.20 Life-threatening illness or organ system dysfunction compromising safety evaluation.
- 3.2.21 Requirement for hemodialysis or peritoneal dialysis.
- 3.2.22 Inability to swallow capsules, malabsorption syndrome or gastrointestinal disease that severely affects the absorption of study drugs, major resection of the stomach or small bowel, or gastric bypass procedure.
- 3.2.23 Known hypersensitivity to drugs chemically related to tivozanib hydrochloride or sunitinib or their excipients.
- 3.2.24 Psychiatric disorder or altered mental status precluding informed consent or protocol-related testing.
- 3.2.25 Patients with clinical symptoms or signs of gastrointestinal obstruction.

4 TREATMENT PLAN

4.1 Overview

This is a single arm phase II trial. All patients will receive 1.5 mg orally of tivozanib given daily for 3 weeks with one week off to complete a 4 week cycle. At the start of each cycle, patients will have a visit with a clinician who will obtain a pertinent history,

perform a physical exam, draw serum CA-125 values and a CBC and CMP and determine if the patient is appropriate for therapy. Treatment will continue until documented disease progression or the patient is unable to tolerate further therapy due to excessive toxicity.

4.2 Study Drug Administration: Tivozanib

- 4.2.1 Drug Dispensing: The patient will be dispensed enough pills for 1 cycle at each monthly visit. Patient pill calendar will be reviewed by study coordinator or nurse. Pill count will be done, and any unused pills will be returned each cycle.
- 4.2.2 Dosing Schedule: Tivozanib hydrochloride will be administered orally, at a dose of 1.5 mg/day, beginning on Day 1 of Cycle 1. Subjects will receive tivozanib hydrochloride once daily for 3 weeks followed by 1 week off treatment. One cycle is defined as 4 weeks. Cycles will be repeated every 4 weeks in the absence of disease progression or unacceptable toxicities.
- 4.2.3 Dosing Information: The prescribed daily dose of tivozanib hydrochloride is to be taken, once per day, preferably in the morning, with water. Tivozanib should be taken on an empty stomach either 1 hour before or 2 hours after meals at the same time each day. The tablets should be swallowed whole and cannot be crushed or broken. Only one capsule of tivozanib hydrochloride should be taken each day. If a dose is vomited or otherwise missed that day for any reason, the dose for that day should not be made up. The next dose should be taken as prescribed at the next scheduled time (i.e., one capsule is to be taken even if the previous dose was vomited or otherwise missed; additional dose(s) should not be taken at any time to make up for any missed dose(s). Grapefruit and grapefruit juice should be avoided during the study.

In the event that tivozanib hydrochloride dosing is interrupted, the duration of cycle/treatment will not be extended; doses missed during the interruption will be captured as omitted rather than delayed.

4.2.4 Dosing Parameters: Subsequent cycles of therapy will not begin (day 1 of each cycle) until the ANC is ≥1500 cells/mcl and the platelet count is ≥ 100,000/mcl. Therapy will be delayed for a maximum of two weeks until these values are achieved. Patients who fail to recover adequate counts within a two week delay will be removed from study therapy. Grade 1 or 2 toxicity will not result in a dose reduction or treatment delay. Drug-related grade 3 or 4 toxicities will result in an interruption in treatment until the toxicity is less than or equal to grade 2. Additionally, a dose reduction will be performed. If there is no recovery to ≤ grade 2 or recurrent grade 3 or 4, then tivozanib will be discontinued.

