4.7.1 Tivozanib Hydrochloride Dose Modification

Clinical judgment will be used to determine appropriate management of the subject experiencing any adverse event (AE). The suggested criteria for dose modification for tivozanib hydrochloride drug-related AEs (excluding hypertension) are summarized in the table below.

Drug-Related	Action Taken	Subsequent Dosing Modification		
Adverse Events				
(excluding				
Hypertension ¹)				
Grade 1	No dose interruption, or reduction	None required; Dosing may continue		
	required; adverse event	at the same dose		
	management is at the discretion of			
	the Investigator			
Grade 2 No dose interruption, or reduction		None required; Dosing may continue		
	required; adverse event	at the same dose		
	management is at the discretion of			
	the Investigator			
Grade 3 ²	Interrupt dosing ³ until toxicity	Dosing may resume at same dose or		
	resolves to \leq grade 1.	reduced dose at the discretion of the		
		Investigator (see below for dose		
		reduction guidelines).		
Grade 4	Interrupt dosing until toxicity	Dosing may resume at same dose or		
	resolves to \leq grade 1.	reduced dose at the discretion of the		
	_	investigator (see below for dose		
		reduction guidelines).		

Tivozanib Hydrochloride Dose Modification Guidelines for Drug-Related Adverse Events

- 1. Hypertension must be treated as described in Appendix C prior to any dose modification
- 2. Referring to toxicity that persists despite appropriate medical care.
- 3. Tivozanib may be interrupted for up to 2 weeks. If a subject is able to resume treatment after an interruption of ≤ 2 weeks, missed doses will not be made up (i.e. the cycle duration will remain unchanged). If any drug related toxicity results in interruption of >2 weeks, the subject should be discontinued from study treatment unless there is clear benefit.

Patients should be followed for assessment of the toxicities until the AEs resolve or are deemed irreversible. The maximum delay of drug administration by the treating investigator or the patients' own decision for any reason, including toxicities, is 2 weeks. If the drug is withheld for more than 2 continuous weeks due to a treatment-related toxicity that does not resolve, the patient will be withdrawn from study treatment. The exception is HTN, which must first be treated as described in Appendix C prior to any dose modification.

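### Sections 4.2.4 and 4.7.1 give conflicting rules for restarting tivozanib after drug-related grade 3 or 4 toxicity, and 4.7.1 contradicts itself on the cycle clock

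*Combined protocol and SAP*

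**What the plan says.** Section 4.2.4 (Dosing Parameters) sets an unconditional rule: "Drug-related grade 3 or 4 toxicities will result in an interruption in treatment until the toxicity is less than or equal to grade 2". It continues "Additionally, a dose reduction will be performed", and it ends treatment if recovery fails or the toxicity returns: "grade 2 or recurrent grade 3 or 4, then tivozanib will be discontinued".

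Section 4.7.1 covers the same ground in a table, introduced with "The suggested criteria for dose modification for tivozanib hydrochloride drug-related AEs (excluding hypertension) are summarized in the table below". For grade 4 the instruction begins "Interrupt dosing until toxicity", and the next line of that cell sets the target at grade 1 or lower; the grade 3 row has the same target. On restarting, both rows say "Dosing may resume at same dose or" and then offer a reduced dose, at the investigator's discretion. Footnote 2 narrows the grade 3 row: "Referring to toxicity that persists despite appropriate medical care". Footnote 3, also marked on the grade 3 row only, says of interruptions of up to two weeks that "missed doses will not be made up (i.e. the cycle duration will remain unchanged". Beyond two weeks it discontinues treatment, with an exception for clear benefit.

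Two paragraphs follow the footnotes. The first withdraws patients from treatment after more than two continuous weeks off drug for unresolved toxicity, and gives no benefit exception. The final paragraph withdraws patients who have not reached grade 1 or lower, or a tolerable grade 2, within two weeks, and does give one. It also has patients resume the current cycle after less than one week off drug, and start a new cycle after one week or more.

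Section 4.7.2 permits reduction for grade 3 or higher events and does not require it.

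**The concern.** A patient with a qualifying event falls under both sections at once, and they direct different actions. Section 11.7 binds sites to the approved text, emergencies aside, and no passage ranks 4.2.4 against 4.7.1. A restart at the same dose is allowed by the table and is a deviation from 4.2.4. A restart at grade 2 is allowed by 4.2.4 and is contrary to the table. Sites can therefore manage the same toxicity differently, and monitors cannot classify deviations consistently.

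The cycle clock matters beyond dosing. Examinations and CA-125 are tied to the start of each cycle (Section 5), and imaging to every other cycle for the first six months (Section 7.1, footnote 11). An unclear Day 1 therefore also makes assessment timing unclear.

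**Working it through.** The plan states no figure on this point. The check is a comparison of texts, followed by simple day counts for the clock.

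**Overlap of scope.** The 4.7.1 table excludes hypertension, and footnote 2 limits its grade 3 row to persistent toxicity. Section 4.2.4 has neither limit. Both therefore apply to non-hypertension drug-related grade 4 events and to grade 3 events that persist despite medical care.

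| Point | 4.2.4 | 4.7.1 table and footnotes | 4.7.1 paragraphs after the footnotes | 4.7.2 |
|---|---|---|---|---|
| Grade at which to restart | 2 or lower | 1 or lower | Final paragraph: withdrawal unless grade 1 or lower, or tolerable grade 2 | Silent |
| Dose reduction | Required | Investigator's choice | Reduced dose settled with the principal investigator and Data Monitoring Committee | Permitted |
| Clock after 1 to 2 weeks off drug | Silent | Unchanged (footnote 3) | Final paragraph: new cycle | Silent |
| Benefit exception | None | Yes (footnote 3) | First: none. Final: yes | None |

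**Restart grade.** Take a grade 4 or persistent grade 3 event that settles at grade 2 and stays there. Section 4.2.4 allows a restart; the table keeps the interruption in force. Past two weeks, footnote 3 (grade 3 row) discontinues treatment unless there is clear benefit, whereas the final paragraph does not withdraw the patient if the grade 2 is tolerable or benefit is seen. Both sections let dosing continue through a new grade 2 event, so the conflict concerns restarting, not dosing at grade 2 as such.

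**Clock.** Footnote 3 covers interruptions of 14 days or less, and the final paragraph starts a new cycle at 7 days or more. Both apply from 7 to 14 days. Let R be the cycle day of resumption, and assume that a new cycle begins on R, which the text does not state.

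- Earliest R: last dose on Day 1, Days 2 to 8 missed (7 days), so R = 9.
- Latest R inside the 21-day dosing window: R = 21.
- Next Day 1: Day 29 of the old count under footnote 3; day R under the final paragraph.
- Difference = 29 − R: 29 − 9 = 20 days, down to 29 − 21 = 8 days.
- Planned dosing days from R to the next rest week: 22 − R under footnote 3, so 22 − 9 = 13 down to 22 − 21 = 1; 21 under the final paragraph.
- If R falls in the rest week (Days 22 to 28), the difference is 29 − 22 = 7 down to 29 − 28 = 1 day. If resumption coincides with the next scheduled Day 1, it is 0 and the two rules agree.

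Section 4.2.3 does not extend the cycle and counts missed doses as omitted. That sits uneasily with the final paragraph but does not directly contradict it.

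**Frequency, for context only.** Section 1.2.3 gives adverse-event interruptions of 18% and reductions of 12% for tivozanib in the phase III renal trial. Applied to 30 patients: 0.18 × 30 = 5.4 and 0.12 × 30 = 3.6. Those rates are not limited by grade, may include hypertension and come from another disease, so they do not count patients caught by this conflict.

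**The case against.** The strongest defence is that the texts differ in force. Section 4.7 relies on clinical judgment, the table is offered as a suggestion and 4.7.2 is permissive, so a site could follow the mandatory 4.2.4 and stay within the guidance. On restart grade and reduction, a course meeting the stricter element of each text would breach neither. That is a statement about logic, not a recommendation, and nothing tells sites to combine the rules. Doing so would also remove the discretion that the table grants. The word suggested does not soften an unconditional requirement in another section.

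It may be said that 4.2.4 concerns blood counts, because Appendix E records that it was moved from a hematologic-toxicity section. The current sentence has no such limit, and the table includes hematologic events anyway.

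On the clock, the final paragraph could mean waiting for the next scheduled cycle, which makes the difference 0. That reading is possible but strained early in a cycle: if dosing stops after Day 1, it omits Days 2 to 21, or 20 dosing days, against the two-week maximum in 4.7.1.

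Some of the objection stands. The benefit-exception point is the weakest, since 4.7.1 is itself uneven. Footnote 3 speaks of stopping treatment while the final paragraph speaks of leaving the study, which Section 4.6 treats as different things. Central approval of the reduced dose limits variation once a reduction is chosen, but it does not settle whether one is required.

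**Conclusion.** The conflict is real and the text is wrong as written. For non-hypertension drug-related grade 4 and persistent grade 3 events, 4.2.4 and the 4.7.1 table disagree on the recovery grade for restart and on whether reduction is compulsory. For grade 3 interruptions of one to two weeks, footnote 3 and the final paragraph of 4.7.1 can both be followed only if resumption falls on the next scheduled Day 1. Section 4.2.4 has no benefit exception where footnote 3 and the final paragraph do. A lesser point is that 4.2.4 does not repeat the hypertension exception in 4.7.1, 4.7.2 and Appendix C.

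The number of patients affected is unknown. The 8- to 20-day clock difference assumes a restart inside the dosing window with the new cycle beginning that day; other readings give 0 to 7 days. Actual exposure is still recorded, and type I error and power are untouched. The case for correction rests on contradictory safety instructions and unclassifiable deviations.

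**What to change.** Reconcile 4.2.3, 4.2.4, 4.7.1 (table, footnotes 2 and 3, and both paragraphs after them) and 4.7.2 into one rule set, or state which section takes precedence. The revised text should settle:

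- the recovery grade required to restart;
- whether reduction is required or discretionary;
- whether the footnote 2 limit on grade 3 applies throughout;
- the cycle clock after one to two weeks off drug, including the day on which a new cycle begins and whether footnote 3 also covers grade 4;
- when treatment stops, whether a benefit exception applies, and whether the patient leaves treatment or the study;
- the hypertension exception.

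Each clinical choice belongs to the sponsor; this review takes no view on which rule is right. The cost is amendment wording, the reviews and approvals in Section 11.2 and distribution to the affiliate sites. No procedures, visits or patients are added.
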